#### PFIZER CONFIDENTIAL

- 1-2 years;
- 2+ years.

The following variables will also be assessed using all available data during the baseline period, unless otherwise noted:

Demographic characteristics:

- Age, continuous, in years, on the date of the cohort-qualifying event;
- Region of residence in the US on the date of the cohort-qualifying date event. Categories of the region of residence will be as follows: Northeast, South, Midwest, or West. Region of residence will not be used as a covariate in Swedish analyses.
- Urbanicity (urban, suburban, rural)
- Calendar year of the index date.
- Duration of baseline period (in months).

Medical comorbidities (Annex 1: Appendix C and Appendix G):

- All-cause cancer (other than endometrial cancer and basal cell carcinoma);
- Breast cancer;
- Ovarian cancer;
- Thyroid cancer;
- Renal cancer;
- Colorectal cancer;
- Endometrial hyperplasia;
- Benign breast lumps (fibrocystic nodule);
- Polycystic ovary syndrome;
- Osteoporosis;
- Osteoarthritis;
- Vasomotor symptoms;

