### 9.3.1. Exposures, Comparators, and Treatment Episodes

GPI codes will be used to identify vaginal estrogen and E+P HT products in the HIRD, (Annex 1: Appendix B) and ATC codes, formulation, brand name, and strength will be used to identify vaginal estrogen and E+P HT Swedish products (Annex 1: Appendix F). Gynecological visits for non-users will be identified in the HIRD using ICD-9-CM and ICD-10-CM diagnostic codes, HCPCS codes for annual exams, CPT codes for pap smear procedures, and physician's specialty code (Annex 1: Appendix C). Gynecological visits will be captured as non-primary outpatient care in the Swedish NPR. Proxies for gynecological visits (i.e., related procedure codes, specialist encounters, and/or reimbursement) will be considered, as appropriate.

Treatment episodes (Annex 1: Appendix I) will be created based on segments of continuous use among the study drug treatment groups, i.e., LDVE, MDVE, HDVC, and E+P HT. Continuous use is defined as consecutive drug dispensings for a treatment group, with no more than 90 days between the end of the days' supply of the earlier prescription and the dispensing date of the next prescription. In order to determine exposure status for vaginal estrogen users during the treatment episode, daily dose must first be computed for each prescription starting with the index dispensing. In the HIRD, daily dose for vaginal estrogen dispensings will be calculated as the drug strength dispensed multiplied by the drug quantity and divided by the days' supply. In Sweden, days' supply is not directly available from the SPDR. Thus, days' supply and daily dose will be estimated for each dispensed vaginal estrogen prescription based on assumptions such as defined daily dose and duration for use. For the E+P HT comparator group, dispensed amount of drug, drug strength and defined daily dose will be used to construct treatment episodes of continuous use. Exposure definitions will be further detailed in the statistical analysis plan (SAP).

The prescription daily doses of the vaginal estrogen dispensings will then be categorized as follows:

- LDVE: <10 mcg/day estradiol or <0.3 mg/day conjugated estrogen;
- MDVE: >10 25 mcg/day estradiol or >0.3 0.45 mg/day conjugated estrogen;
- HDVC: >0.45 mg/day conjugated estrogen.

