### 9.4.2. Swedish Registers, Sweden

The Swedish registry data include five large, nationally held registers: the Swedish NPR, the Swedish Prescribed Drug Register (SPDR), the Swedish Cancer Register (SCR), the Cause of Death Registry, and the Total Population Register (TPR). These registers include data for patients, drugs, cancer, death, and the population linkable by patients' personal identity numbers. Entrance into the registers is upon birth or immigration to Sweden and exit from the registers is upon death or emigration.

Healthcare in Sweden is primarily government-funded and managed at the national, regional, and local level. Only a small proportion of the population (6%) also have some type of supplementary private health insurance. In most regions, there is no formal gatekeeping and patients may contact specialists directly. Applications for data access are sent to the National Board of Health and Welfare and Statistics Sweden and processed by a pre-defined data permit process. The data permit process is preceded by a separate ethical review process by the Swedish Ethical Review Agency. The five Swedish registers are detailed below.

- The Swedish NPR includes information regarding inpatient and outpatient non-primary (i.e., specialist) encounters across Sweden; outpatient general practice encounters are not captured in the NPR. Beginning in 1987, coverage for inpatient admissions became nationwide and is near 100%. Coverage for outpatient non-primary care began nationwide in 2001 and is around 87% (although it may be higher for somatic care such as rheumatology). Key variables include diagnosis, surgery, external causes of injury (E codes), age, sex, hometown, hospital, specialty, and information related to hospital admissions and discharges (e.g., dates, main and contributory diagnoses, mode of discharge). Information on patient anthropometric data (e.g., height, weight, body mass index [BMI]) is not available nor are laboratory test results (e.g., absolute lymphocyte count, blood lipid levels) or clinical measurements (e.g., blood pressure). A number of diagnoses have been reported to have high positive predictive values in the inpatient register. The NPR is updated annually.

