- The SPDR, maintained by the National Board of Health and Welfare, contains information on all prescribed and dispensed medication for patients in Sweden. The SPDR was started in July 2005. The register contains data recorded using personal identification numbers and can thus be linked with other Swedish registers. Coverage of prescriptions is close to 100%, however, inpatient administrations and hospital administered drugs in specialized outpatient care are not captured. Information recorded in the SPDR includes basic demographic characteristics such as age, sex, and residency, as well as medication-specific information such as the prescribed/dispensed drug (e.g., ATC code, International Non-proprietary Names), prescription dispensing date, pack size, dispensed amount, formulation, dosage, prescribing healthcare practitioner, and costs. The SPDR is updated monthly.
- The Swedish Cancer Register was started in 1958 and is managed by the National Board of Health and Welfare. The registry records every cancer case diagnosed by clinical, morphological or other laboratory examinations as well as cases diagnosed at autopsy. Since the mid-1980s there are six regional registries associated with the oncological centers in each medical region of Sweden where the registration, coding and major check-up and

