#### PFIZER CONFIDENTIAL

correction work is performed. The register includes information on patient characteristics, tumor characteristics, diagnosis, and date and cause of death. Data is updated on an annual basis with a lag time of approximately 13 months.

- The Swedish Cause of Death Registry has been maintained by the National Board of Health and Welfare since 1994 and uses the International Classification of Diseases (ICD) coding, but the rules of the World Health Organization. Variables include, date of birth, country of birth, nationality, sex, marital status, date of death, underlying cause of death, and contributing causes of death. Data are updated annually.
- Patient demographics are available from the national TPR, maintained by Statistics Sweden since 1968. The TPR is produced by the Swedish Tax Agency and the data are transferred to Statistics Sweden. The TPR covers all registered individuals in Sweden and their personal identity numbers with 100% coverage. The register includes demographic information related to population size and composition, such as age, sex, marital status, nationality, place of birth, place of residency in Sweden, migrations within Sweden and to/from abroad, births and deaths. The TPR will be used to ascertain length of medical history available for women eligible for the study (i.e., an enrollment file).

Unless specified otherwise, the Swedish registries are updated yearly, and it can take six to nine months to receive a data extraction. As a result, there is a lag in data availability of approximately 12-18 months.

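### The protocol bars region of residence from the Swedish analyses without a reason, although it is recorded and the two arms are identified through different care routes

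*Protocol*

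**What the plan says.** Protocol section 9.3.4 lists region of residence among the demographic covariates, with US categories only: "Categories of the region of residence will be as follows: Northeast, South, Midwest, or West". It then states: "Region of residence will not be used as a covariate in Swedish analyses". No reason is given there or elsewhere.

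Section 9.4.2 shows that the variable exists. The Total Population Register, described as having full coverage, holds "place of residency in Sweden, migrations within Sweden and to/from abroad, births and deaths". The Prescribed Drug Register holds "basic demographic characteristics such as age, sex, and residency".

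The Swedish arms are found in different ways. Users enter on a dispensing in the Prescribed Drug Register, whose coverage is described as close to complete (section 9.4.2). For non-users, section 9.3.1 says: "Gynecological visits will be captured as non-primary outpatient care in the Swedish NPR". Of the patient register, section 9.4.2 says: "Coverage for outpatient non-primary care began nationwide in 2001 and is around 87" per cent, and that general practice is not captured. The same section says that care is managed at national, regional and local level, and: "In most regions, there is no formal gatekeeping and patients may contact specialists directly".

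Section 9.7.1 builds propensity scores from covariates related to the outcome, checks standardized differences for each covariate, and adds those above 0.10 to the Cox model.

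**The concern.** The sentence is a flat prohibition, so it is not a detail left to the SAP. It removes from consideration a demographic variable that the registers hold and that has a plausible link to how the Swedish comparator is assembled. If specialist access or outpatient reporting varies between regions, the regional mix of non-users may depart from that of users.

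The planned safeguards would not reveal this. The balance check in section 9.7.1 works on study covariates, so a barred variable does not trigger it. Section 9.9.1 promises a quantitative bias analysis for residual confounding, but the one specified in section 9.7.4 (item 9) covers only hysterectomy and prior hormone use. Section 9.9.2 adds that ethnicity, socioeconomic status, BMI, exercise, diet and smoking are unavailable in Sweden. Region might partly stand in for some of these.

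At stake are the Swedish LDVE and MDVE hazard ratios and, through section 9.7.5, the pooled ones.

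**Working it through.** **Plan's own figures.** The protocol gives no number for region or for bias from omitting it. Its Swedish study size reproduces: (1.960 + 0.842)² / (0.2 × 0.8 × (ln 1.5)²) = 298.4, so 299 events. Adding a covariate does not change that figure.

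**Step 1: condition for bias.** Omitting region biases the hazard ratio only if, given the retained covariates, (a) the arms differ by region and (b) region predicts endometrial cancer or its detection. The documents make (a) possible. They say nothing on (b).

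**Step 2: size if both hold.** Treat region as binary. Let p₁ and p₀ be the shares of users and non-users in higher-detection regions, and RR the region-outcome ratio given the other covariates. The outcome is rare, so

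bias factor = (1 + p₁(RR − 1)) / (1 + p₀(RR − 1)).

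All inputs are assumptions. With p₁ = 0.50:

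| p₀ | RR 1.0 | RR 1.1 | RR 1.2 | RR 1.3 |
|---|---|---|---|---|
| 0.60 | 1.000 | 0.991 | 0.982 | 0.975 |
| 0.55 | 1.000 | 0.995 | 0.991 | 0.987 |
| 0.45 | 1.000 | 1.005 | 1.009 | 1.013 |
| 0.40 | 1.000 | 1.010 | 1.019 | 1.027 |
| 0.30 | 1.000 | 1.019 | 1.038 | 1.055 |

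Example: p₀ = 0.60 and RR = 1.3 give 1.15 / 1.18 = 0.975.

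Two wider imbalances, with non-users concentrated in higher-detection regions:
- 65% of users and 80% of non-users: 0.986, 0.974 and 0.964 for RR 1.1, 1.2 and 1.3.
- 60% and 90%, RR 1.3: 1.18 / 1.27 = 0.929.

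**Step 3: which imbalances are possible?** Annex 3 assumes that 80% of women with no estrogen or progestogen purchases had a gynecological visit in 2007-2019. Suppose exposure is unrelated to region, so that p₁ is also the population share. The visit probability is then 0.80 × p₀/p₁ in higher-detection regions and 0.80 × (1 − p₀)/(1 − p₁) elsewhere.

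| p₁ | p₀ | Higher-detection regions | Elsewhere | Possible? |
|---|---|---|---|---|
| 0.60 | 0.90 | 1.20 | 0.20 | no |
| 0.65 | 0.80 | 0.98 | 0.46 | near the limit |
| 0.50 | 0.60 | 0.96 | 0.64 | yes |
| 0.50 | 0.55 | 0.88 | 0.72 | yes |
| 0.50 | 0.30 | 0.48 | 1.12 | no |

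If 87% coverage also thins the captured visits, 0.80 becomes 0.80 × 0.87 = 0.696. The 60% versus 90% case still fails (0.696 × 0.90/0.60 = 1.04). So 0.929 and 1.055 drop out under the 80% figure, and 0.964 is close to the extreme.

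**Step 4: set against sampling error.** With 100,800 users matched 1:4, 2.4 years and 70.4 per 100,000, expected events at the background rate are 100,800 × 5 × 2.4 × 0.000704 = 852. The standard error of the log hazard ratio is 1/√(0.16 × 852) = 0.086. A 3% shift is ln 1.03 = 0.030, about a third of one standard error.

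**The case against.** The strongest defence is that the protocol's own selection rule (section 9.7.1) asks for covariates related to the outcome, and nothing in the document links Swedish region to endometrial cancer or its detection. Outcomes come from a national register that records every diagnosed case. If region affects only cohort entry, leaving it out fits that rule. This stands, and it is why bias cannot be asserted. It does not explain a prohibition, however. The same section names demographics among the variables to consider, and US region is listed with no outcome link shown either.

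Three further points stand in part:
- Section 9.9.2 expects women with menopausal problems to be referred to specialist care before vaginal treatment, so specialist access may shape both arms.
- Section 9.3.1 allows proxies for gynecological visits, so the patient register is not necessarily the only way in for non-users.
- Urbanicity, office visits and gynecological visits remain as candidate covariates and may absorb part of any effect. They are imperfect: urbanicity is not region, and the gynecological visit count includes the index date, on which every non-user has such a visit by definition.

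A reader might infer that region determines access to specialists in Sweden, that non-users are therefore over-represented where detection is high, and that the Swedish hazard ratio is pulled downward. The documents do not support this. Section 9.4.2 says only that most regions lack formal gatekeeping, which describes mainly open access. The 87% is a national figure with no regional breakdown. The direction of any imbalance is not given.

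**Conclusion.** The exclusion is explicit, unexplained and not forced by the data. Section 10.1.2 protects place of residency in reporting, which does not prevent its use in a model. Because the arms are identified through different routes, a regional imbalance is possible and the plan as written would not display it.

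Residual confounding of the Swedish and pooled hazard ratios is possible but not shown, and its direction is unknown. It is nil if region is unrelated to the outcome given the other covariates. Otherwise it is probably a few percent at most: about 0.5% to 3% for imbalances of 5 to 10 points and ratios of 1.1 to 1.3. That range rests on assumed inputs, on a two-category region and on no correction by the retained proxies. The limit on imbalance also rests on Annex 3's 80% visit figure and on exposure being unrelated to region. It would loosen if far fewer women had a captured visit.

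This is a modest point, small against the design target of 1.5. It is worth acting on because the remedy is nearly free.

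**What to change.** Delete the prohibition in section 9.3.4. Allow Swedish region of residence at the index date, taken from the Total Population Register, as a candidate propensity score covariate. A workable grouping is the medical regions behind the six regional cancer registries in section 9.4.2. Include it in the section 9.7.1 balance check, with adjustment in the Cox model if the standardized difference exceeds 0.10. If the sponsor prefers to keep it out of the main model, state why and add a region-adjusted sensitivity analysis in section 9.7.4.

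The cost is one more categorical covariate from registers already in the linkage, with no new data source and no change to the stated study size. If region turns out to predict only cohort entry, the loss of precision is trivial. Small regional counts can be suppressed under section 10.1.2.

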### PFIZER CONFIDENTIAL

- Stroke/transient ischemic attack;
- Myocardial infarction;
- Congestive heart failure;
- Coronary heart disease;
- Hyperlipidemia;
- Hypertension;
- Venous thromboembolism;
- Diabetes;
- Major depression;
- Charlson Comorbidity Index;

Prescription medications (Annex 1: Appendix D and Appendix H):

- Selective estrogen receptor modulators;
- Androgens;
- Corticosteroids;
- Lipid lowering agents;
- Antihypertensives;
- Antidiabetics;
- Antidepressants;
- Sedatives/hypnotics;
- Anticonvulsants;
- Antifungals;
- Antivirals;
- Macrolides;

#### PFIZER CONFIDENTIAL

• Immunosuppressants.

Healthcare utilization within the 12 months prior to and including the index date:

- Count of distinct hospitalizations;
- Count of office visits;
- Count of gynecological office visits;
- Count of unique medication classes dispensed;

Other variables within the 12 months prior to and including the index date:

- Pelvic radiation therapy.
- Top 25 most frequently occurring procedures;
- Top 25 most frequently occurring medications
- Top 25 most frequently occurring comorbidities

In the HIRD, the 25 most frequently occurring diagnoses, procedures, and medications among all women in each pre-matched cohort (e.g., LDVE vs. non-users, MDVE vs, non-users, LDVE vs. E+P HT, etc.) within the 12 months prior to and including the index date will be identified using ICD-9-CM diagnosis codes (first four digits), ICD-10-CM diagnosis codes (first four characters), CPT procedure codes (excluding codes for evaluation and management), and medication GPI code (first four digits).

In Sweden, the 25 most frequently occurring diagnoses, procedures, and medications within the past 12 months prior to and including the index date will be identified using International Classification of Diseases, Tenth Revision, Sweden (ICD-10-SE) diagnosis codes (first four characters), procedure codes, and ATC codes. These diagnoses, procedures, and medications are included in the analysis because they may be associated with endometrial cancer and will be considered for inclusion in the propensity score (PS) analysis.

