### 9.1.1. Time Periods

The study period, i.e., the beginning of the baseline period to the end of the follow-up period, is 01 January 2006 (earliest available date) through 31 December 2020 (or most recent available date) in the HIRD, and 01 January 1997 (earliest available date for medical record history) through 31 December 2019 (or most recent available date) in the Swedish registers. The difference between the two data sources in end of study dates is due to the difference in the lag time for populating the HIRD and the Swedish registers.

Ascertainment of exposure and follow-up will be 01 January 2007 - 31 December 2020 (or most recent available date) in the HIRD, and 01 July 2007 - 31 December 2019 (or most recent available date) in the Swedish Registers to allow for a 12- or 24-month baseline period in the HIRD and Swedish data bases, respectively. The index date is the day of initiating a study drug or, for non-users, the date of a gynecological visit that meets all inclusion and exclusion criteria. For new users of vaginal estrogens and E+P HT, a 6-month induction period is allowed following initiation of exposure and prior to beginning follow-up to allow for induction and diagnosis of endometrial cancer (Figure 1). For non-users, follow-up and accrual of person-time starts the day after the index date. The unexposed period before a woman starts any vaginal estrogen will be included as time at risk for a non-user until they begin using one of these drugs. The unexposed time at risk (non-users) will be censored if and when they start using vaginal estrogen, E+PHT or other non-study estrogen or progestogen medications. A sensitivity analysis is included that varies the length of the induction period and includes an induction period for the non-user cohort. Table 1 summarizes the different time periods for the two data sources. Patients may differ in their follow-up dates depending on when they meet the study inclusion, exclusion, and censoring criteria.

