### 9.3.4. Baseline Covariates

The study will identify and describe baseline covariates and prior use of estrogen and progestogen use using all available data prior to and including the index date (see Section 9.1.1 Time Periods). A continuous variable measuring the duration of use will be created for each of the following drug categories:

- Single-entity progestogen contraceptives (oral, transdermal, or injectable);
- E+P contraceptives (oral, transdermal, or injectable).
- Unopposed estrogen hormone therapy: These include oral, transdermal, and injectable singleentity estrogen medications without a progestin dispensed during the baseline period.
- Unopposed progestin hormone therapy: These include oral, transdermal, injectable, and vaginal medications without an estrogen dispensing during the baseline period.
- Progestin opposed estrogen hormone therapy: These include prior use of E+P HT study drugs and subjects who used single-entity estrogen AND single-entity progestin medications during the baseline period (the two medications' usage does not need to overlap).
- Other opposed estrogen hormone therapy: These include prior use of estrogen-testosterone combination medications, conjugated estrogen-bazedoxifene, or the use of single-entity estrogen and single-entity testosterone medications during the baseline period (the two medications' usage does not need to overlap).
- No prior estrogen or progestin hormone therapy use (not including contraceptives). This will be a binary variable indicating no prior hormone therapy use.

Prior contraceptive use may be further divided into categories for time since last dispensing:

• <6 months;

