# 9.7.1. Propensity Score Matching

Details of the statistical methods for PS estimation and matching will be described in the statistical analysis plan. To control for confounding factors, PS will be constructed from baseline covariates for all cohort comparisons. The PS is the estimated probability of receiving a study drug dispensing (i.e., LDVE, MDVE, HDVC), conditional on a set of observed covariates. Propensity scores will be estimated with covariate information collected during the baseline period for each group and each comparison using logistic regression models. Covariates selected will be variables that are related to the outcome, based on literature and clinical judgment as well as sufficiently prevalent in the population to bias the associations under study. Baseline variables to be considered in the model for computing PSs will include demographics, clinical comorbidities, medication use, duration of prior use of hormone therapy, and healthcare utilization (see Section 9.3.4 Baseline Covariates). Propensity score models will also consider for inclusion the 25 most frequently occurring diagnoses, procedures, and medications within the past 12 months among exposed women in the study population that will be ascertained separately in each database. Inclusion of these diagnoses, procedures, and medications in the PS analysis will be based on evidence of association with endometrial cancer in the literature and prevalence.

Comparison groups will be individually matched to exposure groups according to PS to balance the exposure and comparator group on baseline risk factors for outcome at cohort entry. Based on sample size estimates, a matching ratio of 1:4 exposed (e.g., LDVE) to comparator patients (e.g., non-users) is planned. If a 1:4 matching ratio is not possible, 1:3 will be tried, and so on.

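### The 12-month covariate windows in section 9.3.4 include the index date without leaving out the study-drug fill or the qualifying visit, so cohort entry can leak into the propensity score against non-users

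*Protocol*

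**What the plan says.** Section 9.1.1 defines cohort entry: "The index date is the day of initiating a study drug". For non-users it is a gynecological visit meeting the eligibility criteria. Section 9.1.2 requires that non-users have no vaginal estrogen dispensed before that visit or on that day.

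Section 9.3.4 describes baseline covariates in general as measured "using all available data prior to and including the index date". Two narrower blocks follow:

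- "Healthcare utilization within the 12 months prior to and including the index date". This covers hospitalizations, office visits, gynecological office visits and "Count of unique medication classes dispensed".
- "Other variables within the 12 months prior to and including the index date". This covers, among others, "Top 25 most frequently occurring medications".

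Neither block leaves out the index study-drug dispensing or the visit that made a non-user eligible.

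Section 9.7.1 names medication use and healthcare utilization among the variables to be considered for the propensity score. Top-25 items are kept on literature evidence and prevalence. Any covariate whose absolute standardized difference exceeds 0.10 after matching goes into the Cox model.

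The two sections disagree on the ranking population. For the HIRD, section 9.3.4 ranks the top 25 "among all women in each pre-matched cohort". Section 9.7.1 refers to "the 25 most frequently occurring diagnoses, procedures, and medications within the past 12 months among exposed women in the study population".

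**The concern.** A propensity score should rest on what was known before treatment started. A window that closes at the end of the index date takes in the event that defines the group: the first fill for a user and the gynecological visit for a non-user. Two candidate covariates then differ between groups even if the women were identical the day before.

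The class count is the quieter problem. If the score balances the measured count, a user is paired with non-users who take one more other drug class than she does. The balance table checks the measured count, so it would show agreement. The Cox adjustment in section 9.7.1 would not be triggered; if it were, it would adjust for the same contaminated variable. The visit counts carry a similar artefact in the other direction.

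The window also makes the study drug's own class eligible for the top-25 list. A covariate that marks the exposure itself has no place in the model.

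**Working it through.** **Plan's own figure.** The protocol gives no number for this point. Its size calculation is unaffected and reproduces: events = (1.96 + 0.8416)² / (0.2 × 0.8 × (ln 1.5)²) = 298.4, rounded up to the stated 299.

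**Which covariates can capture a vaginal study drug?** (section 9.3.4)

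| Covariate | Captures the index vaginal estrogen fill? |
|---|---|
| Number of distinct drug classes, 12 months | Yes, nothing excludes it |
| Top-25 medications, 12 months | Eligible, nothing excludes it |
| Named classes (SERMs, antihypertensives, antidiabetics and so on) | No, vaginal estrogen is not among them |
| Prior unopposed estrogen | No, oral, transdermal and injectable only |

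**Class count.** Let x be the count without the index study-drug fill. A user's measured count is x + 1, provided she fills no other drug in that class. A non-user's is x. For groups that are otherwise identical, the standardized difference is 1/SD. The SD is not in the protocol, so it is assumed:

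| Assumed SD | 3 | 4 | 5 | 6 | 8 | 10 |
|---|---|---|---|---|---|---|
| 1/SD | 0.33 | 0.25 | 0.20 | 0.17 | 0.125 | 0.10 |

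The artefact exceeds 0.10 for any SD below 10.

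**After matching on that count alone.** Matching sets x(user) + 1 = x(non-user), so x(user) − x(non-user) = −1, or −1/SD in standardized units. A simulation confirms this. Counts had the same distribution in both groups, with 50,000 users and 1,000,000 non-users, exactly matched on the measured count:

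| Mean / SD | Measured difference before matching | True pre-index difference after matching |
|---|---|---|
| 4 / 3 | 0.33 | −0.33 |
| 6 / 4 | 0.25 | −0.25 |
| 8 / 6 | 0.16 | −0.17 |

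This is the extreme case. The planned score has many covariates, so the imbalance that remains is probably smaller.

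**Visit counts.** Every non-user has a gynecological visit on her index date by definition. A user has one on hers only if she happened to attend that day. The built-in shift is 1 minus the share of users with a visit that day, added to the non-users. The protocol gives neither that share nor the SD, so no figure is offered.

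**Top-25 medications.** The study drug's prevalence depends on which section governs:

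- Exposed women only (9.7.1): 100%.
- All women, HIRD at 1:4: 152,941 / (152,941 + 611,764) = 20%. The 611,764 is simply 4 × 152,941, so a larger pre-matching pool would lower this.
- All women, Sweden, using the protocol's estimates: 100,800 / (100,800 + 1,378,928) = 6.8%.

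A test logistic model containing an indicator equal to exposure gave perfect separation and a singular matrix.

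**Secondary comparisons.** Vaginal estrogen and E+P HT users both have an index fill, so the class-count shift is not one-sided there.

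**The case against.** The strongest reply is that the protocol does not commit to using these variables. Section 9.7.1 lists covariates for consideration, screens the top-25 items further, and leaves estimation details to the SAP. It also defines the score as the probability of receiving the study drug given covariates, so an analyst might well drop an obvious exposure marker. This stands as a limit: the defect is that the rule permits the leak, not that the leak is certain. It does not dispose of the point, because the window is stated in the protocol rather than deferred. A class count that is one too high is also much harder to notice than a drug indicator.

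The objection to size is fair too. The SD is assumed, and the full mirror-image imbalance arises only when matching on the count alone. Comorbidities, the Charlson index and individual drug classes are also candidates, and balance is checked for each covariate. No effect on the hazard ratio has been shown.

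Three stronger readings may tempt a reader, and the protocol does not support them:

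- **All drug-based covariates are contaminated.** Only the class count and the top-25 medications can capture a vaginal study drug.
- **The study drug must top the list and separate the groups.** The 100% prevalence holds only under the ranking in 9.7.1. Section 9.3.4 uses four-digit GPI groups (HIRD) and ATC codes (Sweden), and nothing shows that these isolate vaginal estrogen. Section 9.3.1 needs formulation, brand and strength as well as ATC code to identify the Swedish products. Complete separation would also show up as a model failure.
- **The index E+P HT fill counts as prior hormone therapy.** Section 9.3.4 speaks of prior use, section 9.3.1 starts the first treatment episode the day after the index date, and section 9.2.2 assesses earlier E+P HT in its new users before that date.

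**Conclusion.** The point holds in a limited form. As written, section 9.3.4 lets the index study-drug fill into the class count and the top-25 medications, and lets the qualifying visit into the visit counts. In the primary comparisons with non-users, this puts part of the exposure or cohort-entry definition into candidate propensity-score covariates.

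For the class count, the artificial standardized difference is 0.33 to 0.125 for an SD of 3 to 8. This assumes that SD range and that the user fills no other drug in the same class. It compares with a limit of 0.10. What remains after matching on the full score is probably smaller, and the effect on the hazard ratio cannot be derived from the protocol. The disagreement between 9.3.4 and 9.7.1 on the ranking population is a separate inconsistency that stands on the text alone. The required 299 events and the cohort sizes do not change.

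**What to change.** In section 9.3.4 and the covariate program:

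1. Exclude the index study-drug dispensing from the class count and the top-25 medications. Alternatively, end those two windows the day before the index date. The small cost of the alternative is losing same-day fills of other drugs.
2. Exclude the non-user's qualifying index visit from the office and gynecological visit counts. A user's prescribing visit on an earlier day would still count, so the counts will not be perfectly comparable, but the difference fixed by the non-user definition is removed.
3. State once, in both 9.3.4 and 9.7.1, whether the top 25 are ranked among all women in the pre-matched cohort or among exposed women only.

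This takes a few lines of text and a small programming change. It needs no new data and is easiest to make before extraction.
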